## 2 INTRODUCTION

Selumetinib is an oral, potent, and highly selective allosteric MEK1/2 inhibitor with a short half-life that is being developed for the treatment of NF1-PN.

### 2.1 Study Rationale

Selumetinib has been shown to be effective in the treatment of paediatric patients with NF1 who have symptomatic, inoperable PN and is approved in the US for the treatment of paediatric patients aged  $\geq 2$  years of age. Plexiform neurofibromas, whilst typically present at birth, can continue to manifest through late adolescence and early adulthood (Williams et al 2009) and are often associated with significant clinical symptoms including pain and motor dysfunction (Gross et al 2018). As spontaneous PN shrinkage and spontaneous resolution of symptoms associated with PN has been shown to be extremely unlikely (Akshintala et al 2020, Gross et al 2018), adults with NF1-PN continue to have a significant unmet need. This study will aim to inform the benefit risk profile of selumetinib in adults with NF1 who have symptomatic, inoperable PN.

### 2.2 Background

Neurofibromatosis Type 1 is a rare, autosomal dominant genetic disorder that is caused by germline mutations in the NF1 tumour suppressor gene (17q11.2), which encodes the tumour suppressor protein neurofibromin 1. Neurofibromin 1 is a GTPase-activating protein that promotes the conversion of active RAS GTP to inactive RAS guanosine 5'-diphosphate, thereby functioning as a negative regulator of the RAS proto-oncogene, which is a key signalling molecule in the control of cell growth (Gutmann et al 2012). Neurofibromin 1 mutation that leads to loss of function results in a failure to inactivate RAS.

Approximately half of NF1 cases are familial, with penetrance being 100%, and the remainder are the result of de novo (spontaneous) mutations (Evans et al 2010). Features of the disorder typically appear in early childhood and are fully penetrant by adulthood (Stewart et al 2018).

Neurofibromatosis Type 1 is characterised by progressive cutaneous, neurological, skeletal, and neoplastic manifestations early in life and the associated clinical signs and symptoms can be severe. Affected individuals start life with one mutated (non-functional) copy and one functional copy of NF1 in every cell in their body. Although many of the clinical features of this syndrome are apparent from birth, complete loss of gene function is needed for formation of tumours (including PN), by acquisition of a somatic NF1 mutation in selected cells (Gutmann et al 2013; Ruggieri and Packer 2001). Patients with NF1 have an increased risk of developing tumours of the central and peripheral nervous system.

Neurofibromas are benign Schwann cell tumours composed not only of neoplastic Schwann cells but also of non-neoplastic fibroblasts, mast cells, macrophages, endothelial cells, pericytes, and perineural cells. Plexiform neurofibromas are one of the most common benign tumours, occurring in approximately 20% to 50% of patients (Korf 1999; Mautner et al 2008).

Plexiform neurofibromas can have complex shapes and sometimes reach very large size with some documented as being 20% of body weight (Korf 1999; Mautner et al 2008). Plexiform neurofibromas may develop along nerves anywhere in the body.

Patients may have one or multiple PNs that result in clinical impact such as pain, neurological and motor dysfunction, airway compromise, visual impairment, or disfigurement. The severity may range from mild, with modest impact on daily activities, to severe. The symptoms or impact from the presence and growth of PNs are collectively termed PN associated symptoms (also referred to as morbidities in the literature and clinical community) and spontaneous resolution of these symptoms once developed has been shown to be extremely unlikely (Gross et al 2018).

Pain associated with PNs can interfere with daily activities despite analgesia (Wolters et al 2015). Heaney et al 2019 reported the impact of PNs on need fulfilment in adults. Patients reported restrictions on their independence due to the unpredictable nature of their PN symptoms. This results in greater dependence on family and friends, particularly as those with PN-related pain and discomfort found it difficult to devote attention to other issues. This also impacts on their need for role fulfilment as it leads to inability to work or take part in sports or hobbies. The NCI has conducted extensive qualitative research in order to understand the pain experience of adult patients with NF1 and PNs and to modify the standard NRS-11 to be more appropriate for this population. They found that patients with NF1-PN experience two types of PN-related tumour pain- chronic pain and spike pain:

- Chronic tumour pain (also known as usual tumour pain) is tumour pain that is present most of the time (described as “constantly there”, “it’s going to always hurt”, “pain is every single day”).
- Spikes of tumour pain (also known as episodic tumour pain) are sudden bursts of tumour pain that may occur spontaneously or in response to a stimulus (described as “a shock pain”, “like an electricity pain, it will come really fast, and then it leaves”, “if I hit against something”).

The tool developed by the NCI is known as PAINS-pNF and based on the above research has 2 items, one assessing participants' experience of chronic PN-related pain intensity, and the other their experience of spikes of PN-related pain intensity, both for a target PN-location.

Selumetinib is a potent, selective, allosteric inhibitor of MEK that is non-competitive with respect to ATP, licensed for development by AstraZeneca Pharmaceuticals from Array BioPharma. Selumetinib is being co-developed by AstraZeneca and Merck & Co.

Selumetinib blocks MEK activity and inhibits growth of RAF-MEK-ERK pathway activated cell lines. Therefore, MEK inhibition can block the proliferation and survival of tumour cells in which the RAF-MEK-ERK pathway is activated. Neurofibromin-1 (encoded by the NF1 gene) is a negative regulator of RAS and therefore loss of function mutations in NF1 result in activation of the RAF-MEK-ERK pathway. In genetically modified mouse models of NF1 that generate neurofibromas that recapitulate the genotype and phenotype of human type 1 neurofibromas, oral dosing of selumetinib inhibits ERK phosphorylation, reduces neurofibroma volume, proliferation, number and growth. Selumetinib is being developed as a treatment for paediatric and adult patients with NF1 who have symptomatic PNs.

Selumetinib received approval in the US in April 2020 for the treatment of paediatric patients 2 years of age and older with NF1 who have symptomatic, inoperable PN based on the Phase II Stratum 1 data of the SPRINT study (D1532C00057), coordinated by NCI POB under CTEP sponsorship and conducted in the US. Supportive efficacy data were provided by the Phase I data of the SPRINT study (Study 8799; NCI 11 C 0161, D1532C00057).

A detailed description of the chemistry, pharmacology, mechanism of action, efficacy, and safety of selumetinib is provided in the Investigator's Brochure.

## **2.3      Benefit/Risk Assessment**

More detailed information about the known and expected benefits and potential risks of selumetinib may be found in the Investigator's Brochure.

### **2.3.1      Risk Assessment**

The potential risks associated with selumetinib or with the study procedures are shown in [Table 3](#). Guidance and algorithms for the management of these risks are described in [Appendix H](#).

**Table 3 Risk Assessment**

Potential risk of clinical significance	Rationale for risk	Mitigation strategy
Potential risks associated with selumetinib		
Gastrointestinal effects: diarrhoea, nausea, and vomiting	Frequently reported adverse reactions, typically low grade but may require management with dose interruptions and/ or reductions.	Manage with selumetinib dose interruptions and/ or reductions. See Appendix H for management guidelines for diarrhoea.
Retinal toxicity	Isolated cases of RPED, CSR, and RVO in adult patients with multiple tumour types, receiving treatment with selumetinib monotherapy and in combination with other anti-cancer agents, and in a single paediatric patient with pilocytic astrocytoma on selumetinib monotherapy, have been observed.	Exclusion of participants with: current or past history of RPED/CSR or RVO; IOP > 21 mmHg; or uncontrolled glaucoma (irrespective of IOP). An ophthalmologic examination will be evaluated at the times outlined in the SoA, and as clinically indicated. See Appendix H for management guidelines.
Creatine phosphokinase increase	Elevations of CK are predominantly of low grade (1- or 2-grade increase from baseline) and are asymptomatic in the majority of patients. There were asymptomatic Grade 4 elevations in 2 paediatric patients. While there is no established relationship between selumetinib and myopathy, these events should be closely monitored.	Manage with selumetinib dose interruptions and/ or reductions. See Appendix H for management guidelines
Skin toxicity	Rash and dermatitis acneiform are very commonly reported in patients receiving selumetinib monotherapy, but maculopapular rashes have been also observed. Majority of the events are typically low grade and reversible, but may require management with dose modification.	No specific dermatological exclusion criteria are included in this study, however patients with persistent toxicities (CTCAE Grade $\geq 2$ ) caused by previous therapy for NF1 PN, excluding hair changes such as alopecia or hair lightening will be excluded from participation. Dose interruptions and/or reductions. See Appendix H for management guidelines.
Left ventricular ejection fraction decreases	In both paediatric and adult populations taking selumetinib, reversible, asymptomatic reductions in LVEF have been recorded in a small number of patients.	Exclusion of participants with clinically significant cardiovascular disease or LVEF below LLN. Evaluate LVEF at regular intervals as per the SoA, or more frequently as clinically indicated, during treatment. See Appendix H for management guidelines.

**Table 3 Risk Assessment**

Potential risk of clinical significance	Rationale for risk	Mitigation strategy
Transaminase increases	Increases in serum ALT and AST levels have been observed in clinical studies with selumetinib. While the reported events have been typically low grade and no cases of Hy's law have been seen, elevated transaminase is a class effect and should be closely monitored to detect early liver toxicity.	Exclusion of participants with known moderate or severe hepatic impairment. Exclusion of participants with any evidence of severe uncontrolled systemic liver disease, including those with known hepatitis B, hepatitis C, or abnormal liver function test as transaminases $> 2.5 \times$ ULN and total bilirubin $> 1.5 \times$ ULN or $> 3 \times$ ULN in the presence of documented Gilbert's syndrome (unconjugated hyperbilirubinemia). Liver function test monitoring will take place according to the SoA.
Increased BP	Increases in systolic BP and diastolic BP have been observed in clinical studies with selumetinib. Adverse events were generally CTCAE Grade 1 or 2 and asymptomatic, but some patients required amendment or initiation of antihypertensive medication. Study population has increased risk of NF1 vasculopathy, therefore these events should be closely monitored.	Patients with uncontrolled hypertension (at screening: BP $\geq 140/90$ mmHg despite optimal therapy) would be excluded from the trial. Regular monitoring of vital signs is included in the SoA.
Increased exposure in Asian participants	Increased systemic exposure has been seen in adult Asian subjects, although there is considerable overlap with Western subjects when corrected for body weight.	No specific adjustment to the starting dose is recommended for Asian patients, however, these patients should be closely monitored for AEs.

AE, adverse event; ALT, alanine aminotransferase; AST, aspartate aminotransferase; BP, blood pressure; CK, creatine kinase; CSR, central serous retinopathy; CTCAE, Common Terminology Criteria for Adverse Events; IOP, intraocular pressure; LLN, lower limit of normal; LVEF, left ventricular ejection fraction; MRI, magnetic resonance imaging; NF1, neurofibromatosis type 1; RPED, retinal pigment endothelial detachment; PN, plexiform neurofibroma; RVO, retinal vein occlusion; SoA, schedule of activities; ULN, upper limit of normal.

### 2.3.2 Benefit Assessment

Selumetinib has demonstrated compelling ORR, durability of response, improvement in clinical outcomes and symptoms, and quality of life along with a favourable tolerability profile in paediatric patients with NF1 who have symptomatic, inoperable PN. Furthermore, comparable efficacy has been observed in adults based on an ongoing Phase II paired-biopsy study (NCT02407405) in adult patients with NF1 and inoperable PN, sponsored by the NCI. The adult participants in the study may therefore benefit from treatment.

### 2.3.3 Overall Benefit: Risk Conclusion

Taking into account the measures taken to minimise risk to participants participating in this study, the potential risks identified in association with selumetinib are justified by the anticipated benefits that may be afforded to participants with NF1 who have symptomatic, inoperable PN.

Overall, the benefit/risk assessment supports the administration of selumetinib to participants with NF1 who have symptomatic, inoperable PN.

## 3 OBJECTIVES AND ENDPOINTS

**Table 4 Objectives and Endpoints**

Objectives	Estimands descriptions/Endpoints
Primary	
To compare the effect of selumetinib relative to placebo by assessment of confirmed partial and complete response rate (ORR) by end of Cycle 16 using volumetric MRI analysis as determined by ICR (per REiNS criteria) in participants with NF1 who have symptomatic, inoperable PN.	Objective response rate is defined as the proportion of participants who have a confirmed CR (defined as disappearance of the target PN, confirmed by a consecutive scan within 3 to 6 months after the first response) or confirmed PR (defined as a target PN volume decrease $\geq 20\%$ , compared to baseline, confirmed by a consecutive scan within 3 to 6 months after the first response) by end of Cycle 16 as determined by ICR per REiNS criteria. The analysis will include all randomised participants with measurable target PN at baseline per ICR. Data obtained while on-treatment from first dose up until progression (if progression occurs prior to end of Cycle 16), or the last evaluable assessment up to and including end of Cycle 16 in the absence of progression, will be included in the assessment

**Table 4      Objectives and Endpoints**

Objectives	Estimands descriptions/Endpoints
	of ORR. The measure of interest is the difference in ORR. See statistical methods sections for the complete intercurrent events strategy.
Key Secondary	
To compare the effect of selumetinib relative to placebo by assessment of change in chronic target PN pain intensity from baseline in participants with a PAINS-pNF chronic target PN pain score of $\geq 3$ at baseline.	Difference of the means in the change from baseline in PAINS-pNF chronic target PN pain intensity score at Cycle 12 between selumetinib and placebo amongst participants with a PAINS-pNF chronic target PN pain intensity score $\geq 3$ at baseline, and at least one post-baseline average cycle PAINS-pNF chronic target PN pain intensity score, regardless of changes to the participants' chronic PN pain medication (treatment policy strategy). See statistical methods sections for the complete intercurrent events strategy.
To compare the effect of selumetinib relative to placebo by assessment of change in HRQoL from baseline in participants with NF1 who have symptomatic, inoperable PN.	Difference in change from baseline in PlexiQoL total score between selumetinib and placebo at Cycle 12 amongst participants with a PlexiQOL total score at baseline and at least one post-baseline total score. See statistical considerations section 9.4.2.2.2 for the complete intercurrent events strategy.
Secondary	
To demonstrate the effectiveness of selumetinib by assessment of confirmed partial and complete response rate (ORR) using volumetric MRI analysis as determined by ICR (per REiNS criteria) in participants with NF1 who have symptomatic, inoperable PN.	This ORR analysis will include all participants randomised to selumetinib with measurable target PN at baseline per ICR and who received at least one dose of selumetinib, ie, single arm assessment of ORR. Data obtained while on-treatment from first selumetinib dose up until progression, or the last evaluable assessment in the absence of progression, will be included in the assessment of ORR.

**Table 4      Objectives and Endpoints**

Objectives	Estimands descriptions/Endpoints
To demonstrate the effectiveness of selumetinib by assessment of DoR in participants with NF1 who have symptomatic, inoperable PN.	The duration of response will be defined as the time from the date of first documented response (which is subsequently confirmed) until date of documented progression by ICR per REiNS criteria or death due to any cause. The analysis will include all participants randomised to selumetinib with measurable target PN at baseline per ICR who received at least one dose of selumetinib and with a confirmed CR or confirmed PR prior to study intervention discontinuation. Duration of response will be derived using while on-treatment MRI volumetric assessments.
To demonstrate the effectiveness of selumetinib by assessment of PFS in participants with NF1 who have symptomatic, inoperable PN.	Progression free survival is defined as the time from the date of first selumetinib dose until date of progression by ICR per REiNS criteria or death (due to any cause). The analysis will include all participants randomised to selumetinib with measurable target PN at baseline per ICR who received at least one dose of selumetinib. Progression free survival will be derived using while on-treatment MRI volumetric assessments.
To demonstrate the effectiveness of selumetinib by assessment of TTP in participants with NF1 who have symptomatic, inoperable PN.	Time to progression is defined as the time from the date of first selumetinib dose until date of documented objective disease progression by ICR per REiNS criteria. The analysis will include all participants randomised to selumetinib with measurable target PN at baseline per ICR who received at least one dose of selumetinib. Time to progression will be derived using while on-treatment MRI volumetric assessments.

**Table 4      Objectives and Endpoints**

Objectives	Estimands descriptions/Endpoints
To demonstrate the effectiveness of selumetinib by assessment of TTR in participants with NF1 who have symptomatic, inoperable PN.	Time to response is defined as the time from date of first selumetinib dose until the date of first documented objective response (which is subsequently confirmed), by ICR per REiNS criteria. The analysis will include all participants randomised to selumetinib with measurable target PN at baseline per ICR and who received at least one dose of selumetinib and with a confirmed CR or confirmed PR prior to selumetinib discontinuation. Data obtained from first dose up until progression, or the last evaluable assessment in the absence of progression, will be included in the assessment of TTR. Time to response will be derived using while on-treatment MRI volumetric assessments.
To demonstrate the effect of selumetinib relative to placebo by assessment of percentage change from baseline in target PN volume in participants with NF1 who have symptomatic, inoperable PN.	Difference in best percentage change from baseline in target PN volume by ICR per REiNS criteria between selumetinib and placebo during the randomised period. The analysis will include all participants randomised to study intervention with measurable target PN at baseline per ICR. The best percentage change from baseline in target PN volume will be derived using while on-treatment MRI volumetric assessments during the randomised period.

**Table 4      Objectives and Endpoints**

Objectives	Estimands descriptions/Endpoints
To compare the effect of selumetinib relative to placebo by assessment of chronic target PN pain palliation and time to chronic target PN pain palliation in participants with a PAINS-pNF chronic target PN pain score of $\geq 3$ at baseline.	
Chronic target PN pain palliation is defined as improvement of <math>\geq 2</math> in average cycle PAINS-pNF chronic target PN pain intensity score and no increase in chronic PN pain medication compared to baseline for that cycle. Pain palliation will be assessed in participants with a PAINS-pNF chronic target PN pain score of <math>\geq 3</math> at baseline.
 
 
• Difference in proportion of participants with chronic target PN pain palliation between selumetinib and placebo at post-baseline cycles and overall over the randomised treatment period.
 
• Time to chronic target PN pain palliation is defined as the time from the first dose of study drug until the cycle of chronic target PN pain palliation.
 

To compare the effect of selumetinib relative to placebo by assessment of pain medication compared with baseline.	Difference in change from baseline in pain medication use (as reported using the eDiary and as assessed by the investigator) between selumetinib and placebo at post-baseline cycles and overall over the randomised treatment period.
To compare the effect of selumetinib relative to placebo by assessment of pain interference compared with baseline.	Difference in change from baseline in PII-pNF pain interference total score between selumetinib and placebo at post-baseline cycles and overall over the randomised treatment period.
To compare the effect of selumetinib relative to placebo by assessment of physical functioning compared with baseline.	Difference in change from baseline in PROMIS Physical Function scores between selumetinib and placebo at post-baseline cycles and overall over the randomised treatment period.
To compare the effect of selumetinib relative to placebo by further assessment of HRQoL compared with baseline.	Difference in change from baseline in the Skin Sensations domain from the PedsQL (NF1 module acute Version 3.0 – adult report) between selumetinib and placebo at post-baseline cycles and overall over the randomised treatment period.

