#### Objectives and Endpoints

Objectives	Estimands descriptions/Endpoints
Primary  To compare the effect of selumetinib relative to placebo by assessment of confirmed partial and complete response rate (ORR) by end of Cycle 16 using volumetric MRI analysis as determined by ICR (per REiNS criteria) in participants with NF1 who have symptomatic, inoperable PN.	Objective response rate is defined as the proportion of participants who have a confirmed CR (defined as disappearance of the target PN, confirmed by a consecutive scan within 3 to 6 months after the first response) or confirmed PR (defined as a target PN volume decrease $\geq$ 20%, compared to baseline, confirmed by a consecutive scan within 3 to 6 months after the first response) by end of Cycle 16 as determined by ICR per REiNS criteria.  The analysis will include all randomised participants with measurable target PN at

Objectives	Estimands descriptions/Endpoints
	baseline per ICR. Data obtained while on-treatment from first dose up until progression (if progression occurs prior to end of Cycle 16), or the last evaluable assessment up to and including end of Cycle 16 in the absence of progression, will be included in the assessment of ORR. The measure of interest is the difference in ORR. See statistical considerations section 9.4.2.1 for the complete intercurrent events strategy.
Key Secondary	
To compare the effect of selumetinib relative to placebo by assessment of change in chronic target PN pain intensity from baseline in participants with a PAINS-pNF chronic target PN pain score of $\geq 3$ at baseline.	Difference of the means in the change from baseline in PAINS-pNF chronic target PN pain intensity score at Cycle 12 between selumetinib and placebo amongst participants with a PAINS-pNF chronic target PN pain intensity score $\geq 3$ at baseline, and at least one post-baseline average cycle PAINS-pNF chronic target PN pain intensity score, regardless of changes to the participants' chronic PN pain medication (treatment policy strategy). See statistical considerations sections 9.4.2.2 for the complete intercurrent events strategy.

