#### **Analysis Methods**

Full details of the analysis of pain medication use will be documented in the SAP.

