Secondary	Change from baseline in pain medication use (as reported using the eDiary and as assessed by the investigator) at post-baseline cycles and overall, over the randomised period	Subset of the FAS with an evaluable baseline assessment and at least one evaluable post-baseline assessment	Post randomised study intervention discontinuation: hypothetical strategy; prolonged study intervention interruption (greater than 28 days): while on-treatment strategy; early crossover due to documented progression on imaging: while on-treatment strategy; target PN resection: treatment policy strategy	Odds ratio between selumetinib and placebo in decrease in pain medication using random-effect logistic regression model	4.2.11
-----------	--	---	---	---	------------------------

To compare the effect of selumetinib relative to placebo by assessment of pain interference compared with baseline.

Secondary	Change from baseline in PII-pNF pain interference total score at	Subset of the FAS with an evaluable baseline assessment and at least one evaluable	As for the 2 nd key secondary objective	Mean difference between selumetinib and placebo in change from baseline in PII-pNF pain	4.2.12
-----------	--	--	--	---	------------------------

	post-baseline cycles and overall, over the randomised period	post-baseline assessment		interference total score using MMRM with covariates including baseline pain interference total score	
To compare the effect of selumetinib relative to placebo by assessment of physical functioning compared with baseline					
Secondary	Change from baseline in PROMIS Physical Function items at post-baseline cycles and overall, over the randomised period	Subset of the FAS with an evaluable baseline assessment and at least one evaluable post-baseline assessment	As for the 2 nd key secondary objective	Mean difference between selumetinib and placebo in change from baseline in PROMIS Physical Function items and total score using MMRM with covariates including baseline PROMIS item/total score	4.2.13
To compare the effect of selumetinib relative to placebo by further assessment of HRQoL compared with baseline					

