4.2.11.2 Derivations

For both spike and chronic PN pain medication, the analgesic ladder class and the strongest analgesic ladder score for each cycle will be derived following the scoring algorithm presented in Section 3.3.8. For chronic PN pain, changes from baseline (Increased/Decreased/No Change) will also be derived as outlined in Section 3.3.8.

At each cycle, a binary variable will be derived, set to 1 if a decrease in chronic PN pain medication is observed as per definition in Section 3.3.8 and 0 otherwise. A sensitivity definition of this binary endpoint is derived using the secondary definition of decrease from baseline as assessed by the investigator when the reason for the decrease in analgesic requirement is PN pain.

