4.2.11.6 Additional Analyses of Pain Medication

Descriptive analyses of chronic PN pain medication will be produced for the FAS as follows:

- Strongest analgesic ladder category and score at baseline and at each post-baseline cycle,
- A shift table with medication that “increased,” “decreased,” or “No Change” as compared to baseline at each cycle,

Descriptive analyses of spike PN pain medication will be produced for the FAS as follows:

- Strongest analgesic ladder category at baseline and each post-baseline cycle.

Chronic and spike PN pain medications will be listed.

For the investigator assessment of pain medication during the randomised period, descriptive analyses of the number of patients whose medication “increased,” “decreased,” or “No Change” as compared to baseline at each cycle will be shown. The number of patients whose pain medication increased or decreased will also be shown separately by reason.

The analyses on PN pain medication, change in PN pain medication and PN pain medication decrease during the randomised period (except for spike medication) will be repeated for patients in Pain FAS.

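### The protocol's pain medication endpoint covers change in either direction, but the SAP's only inferential analysis of it is the odds of a decrease; no planned analysis estimates the between-arm difference in escalation.

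*Protocol*

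**What the plan says.** - **Protocol, Table 4 (Objectives and Endpoints).** The secondary endpoint is the "Difference in change from baseline in pain medication use (as reported using the eDiary and as assessed by the investigator) between selumetinib and placebo". It is to be assessed both cycle by cycle and across the randomised phase as a whole. No direction is stated.
- **Protocol 9.4.2.3.9 (Pain Medication).** The method is delegated: "Full details of the analysis of pain medication use will be documented in the SAP".
- **SAP 4.2.11.2.** For chronic PN pain, "changes from baseline (Increased/Decreased/No Change) will also be derived as outlined in Section 3.3.8". The section then collapses the three levels to a binary variable, "set to 1 if a decrease in chronic PN pain medication is observed as per definition in Section 3.3.8 and 0 otherwise". The investigator-based sensitivity definition is also decrease-only.
- **SAP 4.2 (endpoint table).** The population-level summary is "Odds ratio between selumetinib and placebo in decrease in pain medication using random-effect logistic regression model". SAP 4.2.11.5 specifies that model, with an odds ratio, 95% CI and p-value at each cycle and overall.
- **SAP 4.2.11.6.** Increased, decreased and no-change counts per cycle are descriptive: "Descriptive analyses of chronic PN pain medication will be produced for the FAS as follows". The investigator assessment is tabulated in the same way, with increases and decreases also split by reason.
- **SAP Section 2.** The listed departures from the protocol analyses do not include the restriction to decreases.

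**The concern.** A change in medication can go up or down, and the protocol asks for the difference between arms in that change. The SAP derives both directions and then models one. A drug that spares participants from stepping up their analgesia, without leading more of them to step down, would have an effect on this endpoint that the planned model cannot register.

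There are two reasons to care. First, the first key secondary estimand takes pain scores regardless of changes in chronic PN pain medication. If placebo participants escalate more, their scores may fall and the pain difference may shrink, so the size of any imbalance in escalation helps in reading that result. Second, the modified WHO ladder in SAP Table 2 has a floor at 0 (no analgesia). The analysis set is drawn from the FAS, which is to include about 40 participants with baseline pain below 3, some of them with no PN pain. Anyone analysed with a baseline score of 0 cannot step down, so for that participant only an increase is informative. The documents do not say how many such participants there will be.

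**Working it through.** **The coding rule.** The documents give no rate, power or sample size for pain medication, so there is no figure to reproduce. The main point follows from the coding:

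| Level derived (SAP 3.3.8) | Value in the model (SAP 4.2.11.2) |
|---|---|
| Decreased | 1 |
| No change | 0 |
| Increased | 0 |

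Moving any number of participants between the last two rows leaves the modelled outcome unchanged. This holds whatever rules SAP Figure 3 uses to assign the levels.

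**Where increases enter the plan.**

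| Place | Use of an increase | Between-arm estimate of escalation? |
|---|---|---|
| SAP 4.2.11.6 | Counts per cycle, eDiary and investigator | No; descriptive |
| SAP 4.2.9 (palliation) and 4.2.10 (time to palliation) | An increase makes the cycle a non-response; arms are compared formally | No; combined with a pain improvement of at least 2 points, Pain FAS only |
| SAP 4.2.2.1.6 | Triggers reversion-to-baseline imputation of the pain score | No; the outcome is pain |

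**Illustration of size.** The inputs are 73 per arm (SAP 3.4), two-sided 5%, one cycle and no covariates. The rates are assumed. Decrease / no change / increase is 10/65/25% on placebo and 10/80/10% on selumetinib.

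- Decrease model: both arms are at 10%, so the odds ratio is (0.10/0.90)/(0.10/0.90) = 1.0. The test rejects in about 5% of simulated trials, which is its alpha.
- Increase model, selumetinib versus placebo: the odds ratio is (0.10/0.90)/(0.25/0.75) = 0.33.
- Power for the increase comparison: the pooled rate is (0.25 + 0.10)/2 = 0.175. The null SE is √(2 × 0.175 × 0.825/73) = 0.0629. The alternative SE is √((0.25 × 0.75 + 0.10 × 0.90)/73) = 0.0617. Then z = (0.15 − 1.96 × 0.0629)/0.0617 ≈ 0.43, so power is about 67%; simulation gives 68%.
- A rank test on the three levels has about 45% power in the same scenario.

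**Range.** Decreases were held at 10% in both arms. Increase rates ran from 20% vs 10% to 30% vs 5%, with 58 to 73 per arm (58 is the PlexiQoL figure after 20% dropout in SAP 3.4). The decrease test stays at 4–5%, and the increase test runs from 32% to 98% (formula).

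**Opposite case.** If only decreases differ (10% vs 25%, increases 10% in both arms), the decrease test has about 68% power and the rank test about 44%. This is a reason to keep the decrease model and not replace it with an ordinal one.

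**The case against.** The strongest reply has four parts.

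1. **Escalation is not ignored.** It is tabulated by arm at each cycle from both sources, it counts as failure in the formally compared palliation endpoints, and it is handled as loss of benefit in a sensitivity analysis of the pain score. This stands. A reader might infer that an effect on escalation would go unseen, or that increases appear only in descriptive tables; the documents support neither. What remains is that the palliation composite cannot separate escalation from pain improvement and leaves out participants with baseline pain below 3, while the counts carry no odds ratio or interval.
2. **The concern about interpreting the pain endpoint is already addressed.** The imputation analysis tests how far escalation affects the pain result. This largely stands, and it weakens the link to the key secondary endpoint. It does not supply an estimate for the medication endpoint.
3. **The protocol delegated the method to the SAP.** This is correct, so choosing a decrease model is within scope. The gap in SAP Section 2 is a matter of transparency, not a breach.
4. **The power figures are assumed.** This stands. The scenario sets decrease rates equal by construction. A reader might infer that a drug which prevents escalation must give an odds ratio of 1; that holds only when decreases do not differ between arms.

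**Conclusion.** The concern holds in a limited form. The one inferential analysis of this secondary endpoint covers decreases only, and no planned analysis isolates the between-arm difference in escalation. That follows from the coding rule without any assumption. The size of the loss does depend on assumptions: about 5% against 68% power in the illustrated scenario, with unseen rates, one cycle and all 73 per arm, in place of the planned repeated-measures model on an evaluable subset. The multiple testing procedure in SAP 3.3.7 covers only the primary and two key secondary endpoints, so no confirmatory conclusion changes. This is a cheap improvement to the completeness of one secondary endpoint.

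**What to change.** In SAP 4.2.11.2 and 4.2.11.5, keep the decrease model and add the same mixed logistic model for a second binary variable: increased = 1, otherwise 0. Use the same covariates, cycles, population and intercurrent event handling, for the eDiary definition and for the investigator definition. Report the overall odds ratio with its 95% CI, with per-cycle results as supportive, all labelled nominal. In SAP Section 2, state how the protocol endpoint is operationalised.

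The cost is SAP wording and one repeated model per definition; the three-level variable already exists. The downside is more unadjusted nominal results. With 12 cycles plus an overall estimate for each of two definitions, full mirroring adds 2 × 13 = 26 odds ratios, which is why the overall estimates should lead. Specifying the model now also avoids a post hoc escalation analysis if the descriptive tables show an imbalance.
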